8 SAFETY INFORMATION AND EXPECTED RISKS

This exploratory study is designed to obtain baseline information to support the potential effectiveness of a standardized postextubation management protocol, utilizing BiPAP and Heated High-Flow Nasal Cannula oxygen (HFNC). BiPAP and HFNC are routinely used at OhioHealth Grant Medical Center; the

research study proposed evaluates these therapies in combination, according to a standardized (2 hours on/2 hours off) protocol.

There are multiple potential physical risks associated with being hospitalized and on mechanical ventilation (Table 1). These risks are present regardless of postextubation management strategies, i.e., assignment to the standardized postextubation management protocol of interest is not considered to add additional risk beyond that associated with routine care. In order to monitor and minimize any potential risks, a Data Safety Monitoring Board (DSMB) will be utilized for this study as outlined in [Section 8.2](#).

Table 1 Potential Adverse Events (AEs) or Serious Adverse Events (SAEs).

Frequency	Mechanical Ventilation ^a	BiPAP/HFNC
Common	Acute lung injury (ALI) Acute respiratory distress syndrome (ARDS) Barotrauma Mortality Organ impairment (hepatic, renal, gastrointestinal, CNS) Sepsis Side-effects of medications (delirium, confusion, agitation) Ventilator-acquired pneumonia (VAP)	Aerophagia (aerophagy) Agitation or delirium Claustrophobia Congestion Dry mouth, nose, and/or throat Other (describe)
Uncommon	Decreased cardiac output Endotracheal tube complications Infection	Breathing difficulty Delayed reintubation
Rare	Damage to trachea, lips, tongue, teeth, vocal cords Tracheostomy	

^a Mechanical ventilation for all patients will be conducted per standard procedures. There are no changes to mechanical ventilation as a result of this research study. All risks associated with mechanical ventilation are present for all patients, regardless of whether or not they are enrolled into the study.

8.1 Risk/Benefit Assessment

While there are common risks associated with being on mechanical ventilation, these risks are independent of the research study. That is, this study is not expected to increase physical risk above that which would be encountered during routine treatment. The only research-related physical risks are

those associated with use of BiPAP or heated high-flow nasal cannula oxygen. These risks are common but are generally mild and reversible (Table 2). Risks will be minimized by ensuring appropriate patient monitoring, including oversight by a Data Safety Monitoring Board ([Section 8.2](#) below).

The only other anticipated research risk is possible loss of confidentiality, which will be minimized by limiting access to study data, storing research-specific data in REDCap, providing only a de-identified data set to the statisticians, and removing identifiers at the earliest possible time point (following non-eligibility determination or at study closure, as applicable).

The information from this study will be used to identify opportunities to standardize processes and identify best practices for mechanically ventilated patients at high risk for reintubation. As such, the potential benefits from the study in the form of knowledge gained are considered to outweigh the risk associated with participation in the study.

Table 2. Risk Assessment			
Category	Risk	Likelihood	Seriousness
Physical	Minimal	Likely	Mild
Psychological	None	Not likely	N/A
Social	None	Not likely	N/A
Legal	None	Not likely	N/A
Financial	None	Not likely	N/A
Confidentiality	Minimal	Not likely	Mild

8.2 Data Safety Monitoring Board

Safety oversight will be under the direction of a Data Safety Monitoring Board (DSMB) composed of individuals with the appropriate expertise, including management of mechanically ventilated patients, trauma patients, and patients with complex co-morbidities. The DSMB will meet approximately monthly, unless other terms are agreed upon by the DSMB, to assess safety and efficacy data for prospectively enrolled patients. The DSMB will operate under the rules of an approved charter (Appendix H) that will be written and reviewed at the organizational meeting of the DSMB. Reporting of DSMB findings will occur in accordance with OhioHealth IRB policy for event reporting as outlined in Section 9 below.

Briefly, in the absence of reportable unanticipated events, DSMB reports will be included for IRB review in the continuing review, while any event resulting in temporary or permanent interruption of study activities to avoid potential harm to subjects will be reported within 48 hours. Any other reportable event will be communicated to the IRB within 10 working days.

9 EVENT REPORTING

9.1 Unanticipated Problems

All events that meet OhioHealth's definition of an unanticipated problem must be reported to the OhioHealth IRB within 10 working days of notification of the event, with the following exception. Any event resulting in temporary or permanent interruption of study activities by the investigator, or DSMB to avoid potential harm to subjects should be reported within 48 hours.

The Principal Investigator will be responsible for determining whether an adverse event (AE) is expected or unexpected, related or possibly related to participation in the research.

9.2 Adverse Events

An adverse event is any untoward or unfavorable medical occurrence in a human subject, including any abnormal sign (e.g. abnormal physical exam or laboratory finding), symptom, or disease, temporally associated with the subject's participation in the research. As outlined above ([Section 9.1](#)), AEs that are unexpected, related or possibly related to the research *and* suggest increased risk will be reported to the OhioHealth IRB.

It is possible that research participants may experience adverse events that do not meet OhioHealth's mandatory reporting requirements (e.g., they are not unexpected, they are not possibly related to participation in the research, they do not place the subjects or others at greater risk of harm). Adverse events that do not meet reporting requirements will be reported to the Data Safety Monitoring Board (DSMB) for review during standing DSMB meetings and summarized for the IRB during the continuing review.

Importantly, for the current study, adverse events associated with mechanical ventilation cannot be related to the study intervention, as study-specific interventions do not occur until the patient is extubated. As such, mechanical ventilation-related adverse events that occur prior to the day of planned extubation will not be reported to the OhioHealth IRB.

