9.3 Definition of a Serious Adverse Event

An adverse event or suspected adverse reaction is considered "serious" if, in the view of either the investigator or sponsor, it results in any of the following outcomes:

- Death;
- Is life-threatening (places the subject at immediate risk of death from the event as it occurred);
- Results in hospitalization or prolongation of existing hospitalization;
- Results in a persistent or significant disability/incapacity or disruption of the ability to conduct normal life functions;

- May (based upon appropriate medical judgement) jeopardize the subject's health and may require medical or surgical intervention to prevent one of the other outcomes listed in this definition. Important medical events that may not result in death, be life-threatening, or require hospitalization may be considered an SAE when, based upon appropriate medical judgment, they may jeopardize the patient or subject and may require medical or surgical intervention to prevent one of the outcomes listed in the above definition.

SAEs must be reported to the OhioHealth IRB if they meet the reporting criteria outlined in [Section 9.1](#). All SAEs must be reported to the DSMB within ten business days.

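### Section 9.2 declares ventilation-associated adverse events unrelated to the intervention without a time limit, although the reason given covers only ventilation before the study extubation

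*Combined protocol and SAP*

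**What the plan says.** Section 9.2 says that "adverse events associated with mechanical ventilation cannot be related to the study intervention, as study-specific interventions do not occur until the patient is extubated". The sentence carries no time limit. The sentence after it draws a narrower consequence: "mechanical ventilation-related adverse events that occur prior to the day of planned extubation will not be reported to the OhioHealth IRB".

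Other parts of the protocol bear on how the first sentence would work:

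- Section 9.1 gives the relatedness decision to one person: "The Principal Investigator will be responsible for determining whether an adverse event (AE) is expected or unexpected, related or possibly related to participation".
- Section 9.2 sends to the IRB those "AEs that are unexpected, related or possibly related to the research", with the further condition that they suggest increased risk.
- Section 9.2 also provides a second route: "Adverse events that do not meet reporting requirements will be reported to the Data Safety Monitoring Board (DSMB) for review during standing DSMB meetings". These events are then summarized for the IRB at continuing review.
- Section 9.3 adds: "All SAEs must be reported to the DSMB within ten business days".
- Section 8.1 says of the risks of mechanical ventilation that "these risks are independent of the research study". The footnote to Table 1 says that they apply whether or not a patient is enrolled.
- Table 1 lists "Delayed reintubation" in its BiPAP/HFNC column as an uncommon risk.
- Section 7.1.3 tabulates adverse events by group on the intention-to-treat population, with no relatedness filter.

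**The concern.** The stated reason is about timing: nothing specific to the study happens before extubation, so a complication of the ventilation that came before cannot be caused by the study. That is sound for the first ventilation episode. The sentence, however, covers ventilation-associated events in general, and this trial expects some participants to be ventilated again after the intervention has begun, because reintubation within 72 hours is its primary endpoint.

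If BiPAP/HFNC can delay a needed reintubation, as Table 1 allows, a ventilator complication after that reintubation is at least possibly related. The class of events is serious: the mechanical ventilation column of Table 1 includes mortality, acute lung injury, ARDS, barotrauma, sepsis and ventilator-acquired pneumonia. At stake are the causality label on such events and, through that label, whether some of them go promptly to the IRB.

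**Working it through.** No figure in the plan has to be reproduced. The check compares the texts, then asks whether the situation will occur.

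**Step 1: scope of the reason against scope of the rule.** The reason in Section 9.2 is that the intervention begins only at extubation. It excludes a causal link for events before extubation and says nothing about later events. The rule has no such limit, so it is wider than its reason by exactly the events that follow reintubation.

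**Step 2: consistency with Table 1 and Section 9.1.** Table 1 names delayed reintubation as a risk of the intervention, which supplies a route from intervention to later ventilator complications. Section 9.1 leaves relatedness to the Principal Investigator, while Section 9.2 answers the question beforehand for a whole class of events. Both cannot be followed for an event after reintubation.

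**Step 3: which reporting routes depend on the label.**

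| Route | Depends on relatedness? | Effect of the sentence after reintubation |
|---|---|---|
| Prompt IRB report (9.1, 9.2) | Yes, with two further conditions: unexpected, and suggests increased risk | Could be closed for an event that meets the other two conditions |
| SAE to DSMB in ten business days (9.3) | No | Stays open; label may read unrelated |
| Other AEs to standing DSMB meetings, then IRB summary at continuing review (9.2) | No | Stays open; label may read unrelated |
| Tabulation by group (7.1.3) | No | None |

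Only the first route can be closed by the sentence.

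**Step 4: will participants be reintubated?** Inputs: 40 participants (Section 5); cited reintubation rates of 12-14% after planned extubation in general and 35-67% in patients aged 65 or over with severe chronic cardiac or respiratory disease, and 19% and 23% in the two arms of a randomized trial of NIV and HFNC in high-risk patients (all Section 3.2).

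Expected number reintubated = 40 × rate:

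- 40 × 0.12 = 4.8 and 40 × 0.14 = 5.6
- 40 × 0.19 = 7.6 and 40 × 0.23 = 9.2
- 40 × 0.35 = 14.0 and 40 × 0.67 = 26.8

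Chance of at least one = 1 − (1 − rate)^40. At 12%: 1 − 0.88^40 = 0.994. At 19%: 1 − 0.81^40 = 0.9998.

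Ventilation after the intervention is therefore near certain to occur. These counts are reintubated patients. They are not ventilator complications, and still less complications due to delay; the documents give no rate for either.

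**The case against.** The strongest reply is that the two sentences in Section 9.2 form a unit. The second follows from the first and limits the explicit IRB exclusion to events before the day of planned extubation, where the logic is right. On that reading the drafters meant only the first ventilation episode. This is probably what was intended, and no text exempts events after reintubation from reporting. But the second sentence limits a reporting exclusion and leaves the causal statement before it unrestricted. Whoever assigns relatedness is still told that a link is impossible.

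A reader might infer that the sentence pre-empts safety reporting or keeps these events from the DSMB. The documents do not support that: both DSMB routes and the tabulation operate whatever the relatedness. Nor is delayed reintubation itself ruled unrelated. Table 1 places it under BiPAP/HFNC, and Section 8.1 treats the risks of those devices as research-related. Only the downstream ventilator complications can be mislabelled.

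Two further points reduce the effect. Table 1 already lists many of these complications as common ventilation risks, so a number of them would fail the condition of being unexpected whatever their cause. And Section 8.1 and the Table 1 footnote describe the background risk of ventilation; they are not instructions for judging events. They do, however, draw no line between ventilation before and after the intervention, so they lend support to the literal reading.

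**Conclusion.** The relatedness sentence in Section 9.2 is wrong as written for ventilation-associated events after reintubation, and it conflicts with Table 1 and with the case-by-case decision in Section 9.1. Followed literally, it mislabels such events as unrelated. It can also withhold prompt IRB reporting from those that are unexpected and suggest increased risk; these would then reach the IRB only in the continuing-review summary.

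The size is limited. One reporting route is affected, for a subset of events whose number cannot be estimated from the documents. The DSMB still receives the events, possibly with a misleading label. The primary analysis is unaffected. The reintubation counts show only that the situation will arise; a reader might take them as the number of patients harmed or misreported, and they are neither.

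The conclusion assumes that staff apply the sentence as it reads, and that the DSMB charter and the data collection tools (listed as appendices, contents not available for this review) do not already separate events before and after the study extubation. The cited reintubation rates come from other populations; the high range is for older patients with severe chronic disease, whereas this trial enrols adults from age 18, and a positive fluid balance can satisfy the risk-factor criterion.

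**What to change.** In Section 9.2, give the relatedness sentence the same time limit as the sentence after it, so that it covers only ventilation-associated events before the planned study extubation. Add that ventilation-associated events after reintubation are assessed case by case for relatedness by the Principal Investigator under Section 9.1, and reported to the IRB when the criteria there are met. Align Section 8.1 and the Table 1 footnote by confining their statements about independence from the study to ventilation before the study extubation. The DSMB routes need no change.

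The cost is a few words of protocol text and relatedness assessments for a small number of patients. No analysis, sample size or data item for the primary endpoint changes.

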9.3 Definition of a Serious Adverse Event

An adverse event or suspected adverse reaction is considered "serious" if, in the view of either the investigator or sponsor, it results in any of the following outcomes:

- Death;
- Is life-threatening (places the subject at immediate risk of death from the event as it occurred);
- Results in hospitalization or prolongation of existing hospitalization;
- Results in a persistent or significant disability/incapacity or disruption of the ability to conduct normal life functions;

- May (based upon appropriate medical judgement) jeopardize the subject's health and may require medical or surgical intervention to prevent one of the other outcomes listed in this definition. Important medical events that may not result in death, be life-threatening, or require hospitalization may be considered an SAE when, based upon appropriate medical judgment, they may jeopardize the patient or subject and may require medical or surgical intervention to prevent one of the outcomes listed in the above definition.

SAEs must be reported to the OhioHealth IRB if they meet the reporting criteria outlined in [Section 9.1](#). All SAEs must be reported to the DSMB within ten business days.

9.4 Clinical Trial of an FDA-Regulated Device

This study meets the FDAAA 801 definition of an "Applicable Clinical Trial" of devices regulated by the United States Food and Drug Administration (FDA) and must therefore be registered on ClinicalTrials.gov. The Principal Investigator or designee will register and activate the study account prior to enrollment, the informed consent form will be posted within 60 days of the last patient enrollment, and all results will be entered within 12 months of the Primary Completion Date (PCD), which is the date of final data collection for the primary outcome measure (e.g., after the last enrolled patient is first extubated, regardless of whether or not they need to be reintubated).

The medical devices used in this study are lawfully marketed in the United States and are being used in accordance with current, FDA-approved labeling for the population of interest (Appendix E). The designed trial is not intended to support a new indication of the devices or to support a change in the labeling. The investigators will obtain IRB approval as well as informed consent before enrolling each prospective patient in the trial.

